## III. Preliminary Studies/Progress Report:

I have developed this paradigm at the NIMH with [name] and have recently published results supporting Aim 1, the association between hostile interpretation bias and irritability, and Aim 2, the association between interpretation bias training and neural response in the threat system, reviewed above. Using these

**Figure 2.** IBT is associated with increased neural activity in response to subtle expressions of happiness, relative to anger, in the bilateral orbitofrontal cortex (OFC) ( $p < .05$  and left amygdala ( $p < .1$ ). Activation during implicit processing of 50% emotion-neutral facial morph, relative to a fixation cross, measured before and after four sessions of daily training. \* $p < 0.05$ , \*\* $p < 0.01$ .

datasets, we completed further, unpublished work to demonstrate that we may feasibly investigate Aim 2 by applying computational models, adapting IBT to fMRI, and collecting data at the University of Colorado Brain Imaging Center. Feasibility of investigating Aims 1 and 2 are sufficient for investigating Aim 3.

***Learning Rate on Active Faces During IBT Differs between Youths with DMDD and Healthy Youths.***

With support from the NIMH Unit on Learning and Decision Making Drs. [name] and [name], we fit a Rescorla-Wagner model filtered through a Softmax equation to measure the learning rate of 13 adolescents with DMDD and 9 youths without psychopathology during four training sessions of IBT. The model detected a between-group difference in learning rate during the first session of IBT (Figure 3). This work provides the foundation for the development of computational models to measure learning and the real-time change in hostile interpretation bias (Aims 1 and 2) and neural correlates (Aim 2) during IBT. It also supports the study design which depends on measuring irritability-associated learning effects during a single session of IBT.

***Neural Activity During Judgments of Ambiguous Face-Emotions.***

In [name] lab, we adapted the hostile interpretation bias assessment portion of IBT to fMRI. We tested the feasibility of using this adaptation with 16 patients, ages 8-17, with diverse mental disorders at the NIMH. These patients tolerated making judgments of these faces sets in sessions lasting at least 28 minutes. We then successfully tested this task on a 24-year-old young adult on the CU Denver MRI scanner. Robust activation in networks of face emotion processing were detected. The work demonstrates that blood oxygen-level dependent (BOLD) signal during judgments of ambiguous faces may be measured in adolescent patients.

#### IV. Research Methods

##### A. Outcome Measure(s):

[figure not shown]
***Hostile Interpretation Bias.*** Hostile interpretation bias is measured by the tendency of individuals to judge ambiguous face-emotions as angry. The "balance point" is a common measure of hostile interpretation bias (Figure 1). It is the point along a happy-angry continuum of face-emotions where judgments switch from predominantly happy to angry.

***Learning Rate.*** Learning rate is parameter in the Rescorla-Wagner model that estimates how quickly an individual learns to switch their responses.

***Neural Activity.*** Neural activity is measured by the amplitude of the blood-oxygenation level dependent (BOLD) signal during functional magnetic resonance imaging (fMRI).

***Neural Connectivity.*** Neural connectivity refers to the coordinated activity between cortical and subcortical neurons. It is measured by the covariance of BOLD signal during fMRI. Specifically, the amplitude of covariation by task condition in linear models.

***Irritability.*** Within this study, irritability will be analyzed as a dimensional construct along the Affective Reactivity Index (ARI). Several prior reports of ARI scores and variance in different cohorts of youths with anxiety disorders, attention-deficit hyperactivity disorder, and DMDD strongly suggests that our recruitment strategy will guarantee a broad variability in ARI scores.

**Figure 3.** The trajectory of learning benign interpretations of angry faces differs between patients with DMDD (red) and healthy youth (blue), suggesting irritable youth are slower learners than nonirritable youth in IBT. Plotted values are the fixed effects estimates of learning from the mixed-effects ANOVA (Group by Session effect,  $p=0.03$ ). The largest difference was within the first session ( $t(20)=1.88$ ,  $p=.08$ ., Cohen's  $d=0.84$ , a large effect).

## B. Description of Population to be Enrolled:

We request a pilot group of up to 10 participants to establish the procedure and ensure the fMRI IBT training work wells at the UC Denver Brain Imaging Center in irritable youth. This study will target the total accrual of 100 youths, ages 13-17 years, drawn from a clinical sample, with at least mild, clinically significant irritability, typical intellectual functioning (IQ>80), absence of major medical problems, including head trauma. We anticipate 126 individuals may be enrolled allowing for 21% attrition and/or data loss. The total accrual target of 136 probands, who each require at least one caregiver to be involved, but we will not prevent another parent from participating. We will encourage one caregiver to fill out measures, as they are repeated measures. Based on prior experience, about 1.5 caregivers will be involved, yielding about 340 individuals on whom we will have collected information and 250 (100 probands plus 150 caregivers) who will be enrolled to generate sufficient data.

Additionally, we will recruit a small subsample from the same clinical population but with low irritable mood youth defined as parent-report ARI<3 and self-report ARI<2. Three volunteers will be uniformly assigned to each arm of the study at random.

Exclusionary diagnoses include current posttraumatic stress as well as lifetime bipolar I, II, cyclothymic, psychotic, and autism spectrum disorders. The rationale for these exclusions are to minimize confounds due to disorder-specific, face-emotion processing impairments or traumatic events. Exclusion criteria include clinical judgement of psychiatric instability and clinical high-risk status for danger to self or others. Exclusionary criteria include pregnancy. To operationalize some instability, any mental health treatment changes, new prescriptions of psychoactive medications, or substance use within 4 weeks of trial start will be considered exclusionary. Participants will be informed of these requirements during scheduling. A focus on adolescents maximizes comparison to prior work, ensures a more homogenous developmental level of face-emotion processing ability, and reduces age-related motion during fMRI or inattention to task.

Recruitment will take place through an established recruitment network across several clinical sites within the Children's Hospital Colorado Network of Care (CHCO NOC), University email and social media announcement(s), postings on our lab website and [childrenscolorado.org](http://childrenscolorado.org), and ResearchMatch (Materials Attached).

BuildClinical, a platform for academic researchers to accelerate clinical research recruitment, will also be used to distribute approved advertisements on their website and affiliated social media accounts.

Participants may contact study personnel via email or telephone call. Then, a telephone screen by Drs. [name] or [name] with the adolescent's parent or guardian will address standard MRI, study-specific exclusions, and likelihood of having clinical irritability (Attached). This screen has been designed to reduce the chance that an adolescent participant will be ineligible for randomization to a study arm after Assessment.

If [name] or [name] do not identify an exclusion and clinically significant irritability is likely, they schedule two study visits with the family, at their convenience, to ensure clinic and scanner availability.

## B. Study Design and Research Methods

Participants will complete two study visits and one online assessment, with procedures listed in this table and described below.

### Assessment, Visit 1, Day 1

This visit will occur at the Pediatric Mental Health Institute (PMHI) outpatient clinic in a private laboratory room (see COMIRB Application, Section Q, for facilities description).

Adolescents and their parent will begin with a session to obtain informed consent and assent with study personnel (see COMIRB Application, Section L, for procedure). Clinical assessment will begin with the parent and adolescent will each complete their respective versions of the Affective Reactivity Index (ARI) to

Clinical Assessment	Training	Post training Assessment
Day 1	Up to Day 7	1 week ± 3 days after training
Clinic	Clinic	Online
Consent	IBT	ARI
ARI		Scales
WASI		
KSADS		
C-SSR		
Scales		

measure level of irritability. Adolescents with mild clinical irritability will be invited to continue (parent-report ARI  $\geq$  3 or self-report ARI  $\geq$  2; based on sensitivity analyses in Kircanski et al.).

Adolescents and their parents will complete a semi-structured diagnostic interview about the adolescent with Drs. [name] or [name] using the computerized Kiddie-Schedule for Affective Disorders and Schizophrenia, Present and Lifetime Version, (KSADS-PL) updated for DSM-5 and the Columbia-Suicide Severity Rating Scale (C-SSR; PMC 3893686). This will allow for diagnostic characterization of the sample, and the evaluation of exclusionary diagnoses. Pubertal development will be assessed using Tanner's Sexual Maturation Scale. Adolescents will also complete the Wechsler Abbreviated Scale of Intelligence- 2nd edition (WASI-II), which provides a full-scale intelligence quotient (IQ) estimate based on the administration of two subtests: Vocabulary and Block Design. During the initial clinical assessment and in the post training assessment, clinical characteristics will also be assessed using self- and parent report scales of depression (Short Moods and Feelings Questionnaire), anxiety (Screen for Child Anxiety Related Emotional Disorders), ADHD symptoms (SNAP-IV, PMID 11211365), anger (State-Trait Anger Expression Inventory 2, Child and Adolescent Version), and irritability (Brief Irritability Test (BITe)). In response to the COVID-19 pandemic, we will also be assessing COVID-related stress using pediatric and parent reports via the Patient-Reported Outcomes Measurement Information System (PROMIS) Physical and Psychological Stress 8a and the Coronavirus Impact Scale (CIS).

During this visit, adolescents will complete the following self-report forms via RedCap:

1. Short Moods and Feelings Questionnaire (MFQ; 2 minutes)
2. Screen for Childhood Anxiety Related Emotional Disorders (SCARED; 8-10 minutes minutes)
3. Affective Reactivity Index (ARI; 2 minutes)
4. State-Trait Anger Expression Inventory-2 Child and Adolescent (STAXI-2 C/A; 5-8 minutes)
5. Brief Irritability Test (BITe; 2 minutes)
6. PROMIS Pediatric Short Form – Physical & Psychological Stress Experiences 8a (3-5 minutes)

During this visit, caregivers will complete the following parent-report forms via RedCap:

1. ARI (2 minutes)
2. SCARED (8-10 minutes)
3. MFQ (2 minutes)
4. SNAP-IV, items 1-40 only, (5-10 minutes)
5. PROMIS Parent Proxy Short Form – Physical & Psychological Stress Experiences 8a (3-5 minutes)
6. Coronavirus Impact Scale (2 minutes)

All forms are included in the Appendix. Based on our pilot, we estimate the total time for Visit 1 to take 3-3.5 hours.

*While COVID-19 safety procedures are still in effect on the Anschutz Medical Campus, the following adaptations may be made to Assessment, Visit 1, Day 1:*

The first study visit may be conducted completely over telehealth through a University-approved and CHCO-compliant audio/video application. Informed consent and assent will be obtained remotely using REDCap's eConsent framework. All measures will be administered virtually. Tanner and the STAXI-2 C/A will be omitted for individuals conducting Visit 1, Day 1 via telehealth as online copies of these measures are not available.

The first study visit may also be split between in clinic and telehealth appointments. The clinic and telehealth appointments will occur within 48 hours of each other. Staff, adolescents, and caregivers will maintain CHCO safety procedures at all times in the clinic.

#### Randomization

Within 48 hours of Visit 1, Drs. [name] or [name] will determine if any exclusion criteria are met. This time allows Drs. [name] and [name] to consult each other or clarify information with the participants to achieve consensus for any unclear exclusionary diagnosis. If so, [name] will call the participants to thank for their participation, inform them of their exclusion, and cancel their second visit. Some exclusionary criteria are not stable, and it is likely the participants will be eligible during the study period. In that case, participants will still be

marked as a “Screen Failure,” in the consented, but not enrolled, category. However, they will be offered the opportunity to reschedule in the future. In this case, the participants will need to repeat visit 1.

During the pilot phase, eligible adolescents will not be randomized to a study arm, but will be invited to follow procedures for any arm. After pilot, eligible adolescents will be randomized for a 2 x 2 factorial, single blinded, randomized controlled trial, eligible adolescents will be assigned to one of four arms representing TRAINING (active or sham IBT) and SCANNING (in- or out-of-scanner IBT). First, scan ineligible patients will be assigned to out-of-scanner training. Second, randomization will use established minimization procedures (R packages randPack and/or randomizeR) to ensure the four arms are similar in terms of sex, age, socioeconomic status (SES), and IQ. The single blind is required so I may track adolescents with acceptable data. Acceptable behavioral data are at least 70% accuracy on extreme morphs (see [name] et al. for the development of this threshold) and, if applicable, scans of acceptable quality (see below). Allocation to any arm will end when the accrual goal of 25 adolescents with acceptable data have been reached for a total N=100. Since this is a small trial that is not intended to assess clinical efficacy, promoting power and ensuring balance across confounds outweigh the potential for allocation bias due to single-blinding or minimization procedures.

#### Training, Visit 2, Up to Day 7

For those randomized to out-of-scanner conditions, this visit will occur at the Anschutz Medical Campus Gary Pavilion outpatient psychiatric clinic in a private laboratory room. For those randomized for in-scanner conditions, this visit will occur at the Anschutz Medical Campus Brain Imaging Center (BIC). See COMIRB Application, Section Q, for facilities description. See COMIRB Application, Section J, for MRI safety screening procedures.

At the start of the second visit, adolescents will complete an out-of-scanner interpretation bias assessment on a laptop approximately 3 minutes. Adolescents will then complete an in- or out-of-scanner session of active or sham IBT depending on their allocation (approximately 18 minutes). Immediately after IBT, all adolescents will complete an out-of-scanner interpretation bias assessment presented on a laptop. To assess whether training on the ‘prototypical’ male face-set generalizes to other face-sets, adolescents will complete another interpretation bias assessment designed by [name] and colleagues. It has nearly identical trial structure, but uses four NimStim^63 face-identities that differ in gender and race along the same 15-morph continuum and takes 7.5 minutes to complete. Details of these cognitive tasks and image acquisition are provided below.

At the end of this session, we will give participants a RedCap link and log on instructions. We will ask them to complete an online assessment via RedCap in one week. For those who opt against completing their assessment online, we will give them a packet of assessment measures.

Based on pilot experience at the NIMH, I anticipate the visit length for each out-of-scanner arm to be one hour long and the visit length for each in-scanner arm to be two hours.

*While COVID-19 safety procedures are still in effect on the Anschutz Medical Campus, the following adaptations will be made to Training, Visit 2, Up to Day 7:*

Adolescents and their caregivers will be screened for COVID-19 symptoms the day before their scheduled Visit 2 in accordance with CHCO site standards or BIC standards, depending on randomization.

Visit 2 appointments occurring at the Gary Pavilion outpatient clinic will adhere to all CHCO site safety procedures. Staff, adolescents, and caregivers will maintain CHCO safety measures at all times in the clinic. Alternatively, Visit 2 appointments at the Brain Imaging Center will adhere to all BIC/University COVID safety procedures. Staff, adolescents, and caregivers will maintain BIC safety measures at all times in the building.

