the adolescent does not become overly frustrated. Prior use of these tasks has shown that children with clinically significant irritability are generally able to complete these tasks without difficulty or significant negative affect.

With regards to fMRI, some children may become nervous or uncomfortable during MRI scanning. High noise environment is a risk of fMRI and all adolescents are required to wear ear protection. All adolescents are warned of unusual sensations during fMRI which are possible due to nerve stimulation. Standard MRI metal screens and MRI-safe gowns will be employed to ensure no ferromagnetic or electronic material will be brought in by the participant into the scanner. A number of procedures have been established to reduce the discomfort of adolescents during neuroimaging protocols (see Protection Against Risks below). As with all Brain Imaging Center protocols, every effort will be made by Brain Imaging Center personnel to engage adolescents by creating a pleasant and positive atmosphere. In the event that a child cannot complete the assessment in the allotted time, an additional day of testing may be scheduled if agreed to by the child and parent/guardian.

Consistent with Brain Imaging Center protocol, a urine pregnancy test will be given to adolescent females to prevent incidental research MRI scan of pregnant subjects. Pregnancy is an exclusion criterion for the study and this will be discussed during the informed consent process. Families will be notified that positive pregnancy screening results will be disclosed to the adolescent only to conform with the Colorado minor consent and confidentiality law. Pregnant adolescents will be excluded from all arms of the study, due to the high likelihood that a positive test will result in acute distress that may confound the study due to a systematic assignment of distressed, pregnant adolescents to the non-MRI arm. Consultation of a positive result will be with a licensed clinician on call for the scan to provide consultation on the interpretation of a positive urine pregnancy screen, rights, and referrals. Pregnant females may re-enroll when they are no longer pregnant.

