#### **F. Data Analysis Plan:**

Development of Computational Models. The application of computational models of learning to behavior and neural response is integral to both the training and scientific aims of this proposal. We will apply well-established models of human reinforcement learning (variants of Rescorla-Wagner and Pierce-Hall that incorporate stimulus generalization) and assess their fit to IBT data. Goodness of fit will be assessed with expectation-maximization and maximum-likelihood algorithms. Models will also be tested in secondary analyses of IBT data of youths with DMDD from [name] lab. The parameters for the model will be (a) parameters determining initial value, i.e. probability of angry, for each stimulus, (b) learning rate, (c) a parameter determining degree of generalization among stimuli, (d) reliability of judgments (inverse choice temperature). Simulation of the model under parameters estimated from the data will yield predictions for the trialwise likelihood that each face is considered angry and of the trialwise prediction error. (Note: these last two variables could be used as predictors in the fMRI analysis.) For transparency, analytic code (not any data) for all models will be posted to online software development repositories.

Hypothesis Testing. To maintain rigor, all analyses will involve omnibus models with appropriate diagnostics for model fit and influential data. Minimization procedures should ensure balance on the environmental and biological factors (sex, age, SES, and IQ) that may influence hypothesized associations. Additional potential factors are anxiety, depression, pubertal development, and in- or out-of-scanner training. The effects of all of these factors on independent variables will be assessed. If an imbalance across training groups occurs in any of these factors or a significant association is detected between these factors and an independent variable, it will be entered into the omnibus model as a covariate.

Hypothesis 1.1: Baseline hostile interpretation bias is associated with baseline irritability. Linear regression with pre-training balance point (interpretation bias) as a dependent variable and pre-training ARI (irritability) as an independent variable.

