Hypothesis 1.2: Active but not sham, IBT will reduce hostile interpretation bias. Mixed-effects linear regression with balance point (interpretation bias) as a dependent variable and training condition (active vs. sham), and time of interpretation bias assessment (pre- or post-training) as independent variables of interest and person as a grouping variable and random effect. Similar models will test for group differences in active or sham IBT on other measures of hostile interpretation bias after training.

Hypothesis 2.1: The rate of learning new associations to ambiguous faces training will be associated with baseline irritability. For those in the active condition, linear regression will test the association between pre-training ARI (irritability) and learning rate to reversal feedback of baseline angry judgments to the two ambiguous morphs.

Hypotheses 2.2 and 2.3: Active, but not sham, IBT will evoke greater neural response in threat-learning systems. For each person, learning will be modeled with regressors coding the “value” or trialwise likelihood that a participant considers the morph to be angry. The amplitude of BOLD %signal change (activity) or amygdala covariance (generalized psychophysiological interaction; connectivity) related to these regressors represents neural response to value. Critically, these regressors represent learning itself where value is changing towards benign judgments in the active training condition to two ambiguous morphs. These will be carried forward to the second level mixed-effects linear models of the effects of morph by pre-training ARI by training condition. A voxel-wise threshold of  $p < .001$ , whole-brain, cluster corrected to  $p < .05$  via permutation testing or Monte Carlo simulation as appropriate, will be used to identify significant associations. A three-way interaction of change in value by morph by training condition will indicate neural areas where learning is influenced by irritability in active but not sham training of reversals of ambiguous morphs. In addition, our *a priori* identification of the likely role of the amygdala, OFC, and ACC justifies follow-up region-of-interest analyses of mean activity or connectivity extracted from these areas with the same omnibus mixed-effects model.

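### SCANNING is randomised only among scan-eligible adolescents, and Hypothesis 2.1 pools both settings without a setting term that the covariate rule would reliably add

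*Combined protocol and SAP*

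**What the plan says.** The Randomization section presents a single-blind 2 x 2 factorial with four arms defined by TRAINING (active or sham) and SCANNING (in or out of the scanner). Allocation has two steps. The first is "First, scan ineligible patients will be assigned to out-of-scanner training". The second is minimisation "to ensure the four arms are similar in terms of sex, age, socioeconomic status (SES), and IQ". Neither scan eligibility nor ARI is a minimisation factor. Arm sizes are fixed: "Allocation to any arm will end when the accrual goal of 25 adolescents with acceptable data have been reached for a total N=100".

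Three other places bear on who is scan-ineligible. The telephone screen (B. Description of Population to be Enrolled) "will address standard MRI, study-specific exclusions, and likelihood of having clinical irritability", and visits are booked if no exclusion is found. Section C keeps adolescents with certain implants or metal fragments out of the MRI portion only. Section C also excludes pregnant adolescents from every arm, because a positive test is likely to cause acute distress "that may confound the study due to a systematic assignment of distressed, pregnant adolescents to the non-MRI arm".

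For Hypothesis 2.1, F. Data Analysis Plan states: "For those in the active condition, linear regression will test the association between pre-training ARI (irritability) and learning rate". No setting term is given. Setting is listed among the possible covariates, but a factor enters only if it is imbalanced across training groups or if "a significant association is detected between these factors and an independent variable, it will be entered into the omnibus model as a covariate".

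**The concern.** A reader of the factorial description would take SCANNING to be randomised for everyone. It is not: a scan-ineligible adolescent has no chance of in-scanner training, and the protocol does not state that limit on the claim. Any contrast of in-scanner with out-of-scanner training in the full sample would mix the setting with scan eligibility.

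The planned analysis most exposed is Hypothesis 2.1. Training inside a scanner may change how quickly adolescents learn. If so, the pooled regression carries that difference as unexplained variance. If ARI also differs between settings, the difference enters the slope. The covariate rule is the only safeguard, and it looks at the wrong variable. The setting is balanced across training groups by design, so the imbalance trigger should not fire. The other trigger tests setting against the independent variable, taken here as ARI (its role in Hypothesis 1.1), and not against learning rate.

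**Working it through.** **The plan's own figure.** Using Fisher's z, power = Φ(atanh(r)·√(n − 3 − k) − z), with k covariates. Aim 1 with r = .25, n = 100, one-tailed .05: .2554 × √97 − 1.645 = 0.871, giving 80.8%. The stated 80% reproduces.

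**Hypothesis 2.1 on its stated analysis set.** The pilot learning difference (Figure 3 caption) is d = 0.84, so r = .84/√(.84² + 4) = .39. Sidedness is not stated for this hypothesis; two-sided .05 is assumed.
- Active only, n = 50, no covariate: .4118 × √47 − 1.960 = 0.863, power 80.6%.
- The same with setting in the model (k = 1): .4118 × √46 − 1.960 = 0.833, power 79.8%. The extra term costs 0.8 points if there is no scanner effect.
- n = 25 (in-scanner active only): 48.9%. n = 100: 98.2%.

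**What the allocation rule does.** The ineligible fraction f is not in the documents and is assumed. With 50 of 100 places in-scanner, the ineligible share of the out-of-scanner arms is 2f, and an eligible adolescent's chance of scanning is 0.5/(1 − f).
- f = 2%: 4% and 0.51.
- f = 10%: 20% and 0.56.
- f = 20%: 40% and 0.63.
- f = 30%: 60% and 0.71.

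**Loss from omitting setting, with no ineligible patients.** Set the residual SD of learning to 1. The slope is then .39/√(1 − .39²) = .4235, and a scanner effect e with 25 v 25 adds variance e²/4. The pooled correlation is .4235/√(1 + .1794 + e²/4).
- e = 0.5: r = .380, power 78%.
- e = 0.8: r = .366, power 75%.
- e = 1.2: r = .341, power 68%.

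**Simulation with the covariate rule applied.** Each trial has 25 in-scanner and 25 out-of-scanner active participants, a negative ARI slope and a scanner that lowers learning. Setting is added only if it is associated with ARI at p < .05.

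| Scanner effect (SD) | None ineligible, as written | 20% ineligible, ARI +0.5 SD, as written | SCANNING always in |
|---|---|---|---|
| 0.5 | 79% | 77% | about 81% |
| 0.8 | 76% | 72% | about 81% |
| 1.2 | 70% | 63% | about 81% |

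Against 81%, the total loss at 20% ineligible is 4, 9 and 18 points. Of this, 2, 5 and 11 points are present with nobody ineligible; scan-ineligibility adds about 2, 4 and 7. The ARI trigger adds setting in only about 10% of trials at 20% ineligible. If the ARI slope has the opposite sign, power as written at 20% ineligible is about 79 to 83%, so little is lost. With no ineligible patients the loss does not depend on the sign.

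**False positives.** In this scenario type I error stays near 5% (at most about 6%). It rises only if ineligible adolescents also differ in learning itself. At the extreme of the range tried (20% ineligible, 1 SD higher on both ARI and learning, 0.8 SD setting effect), the spurious correlation without adjustment is .18 and type I error 25%. Adjusting for setting alone leaves .11. Nothing in the documents suggests differences of that kind.

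**The case against.** The strongest reply is that little depends on this. No stated hypothesis tests SCANNING. Hypothesis 1.2 compares active with sham, which stays randomised within each setting. The protocol states the rule directly after naming the factorial. All of that stands.

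Several stronger readings are tempting, and the documents do not support them.
- A reader might infer that the two settings hold different kinds of patient. The only scan exclusions that Section C names for the MRI portion are implants and metal fragments, and nothing links these to ARI or learning.
- A reader might take the pregnancy exclusion as an admission that scan-ineligibility in general confounds the study. Its stated reason is acute distress after a positive test, which other ineligible adolescents do not share.
- A reader might see a contradiction between the telephone screen and the allocation rule. The screen can be a first filter, with the rule as a fallback for cases found later. On that reading the ineligible fraction is probably small.
- A reader might attribute the whole power loss to the allocation rule. At least half of it arises with nobody ineligible.

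It may also be said that the covariate rule meant the dependent variable, or that learning rate is the independent variable in this regression. Even then, a 25 v 25 comparison detects a 0.5 SD difference only about 42% of the time, so a significance trigger remains a weak safeguard.

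**Conclusion.** The point holds as a limited one. SCANNING is randomised only among the scan-eligible, and the protocol should say so. Hypothesis 2.1 as written pools two settings, and the covariate rule would not add setting in response to a scanner effect on learning rate.

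The consequence is a possible loss of power, not a demonstrated bias. It is about 2 to 11 points from setting variance alone, and about 4 to 18 points if 20% are ineligible with higher ARI and the slope is negative. The true correlation is borrowed from a small pilot. The ineligible fraction, the ARI shift and the scanner effect are all assumptions. With a small scanner effect the loss is negligible. Hypothesis 2.1 has only about 81% power at n = 50 under the pilot effect, so there is little margin.

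All of this applies if Hypothesis 2.1 uses both settings, as F. Data Analysis Plan says. The Specific Aims place Aim 2 beside the fMRI subsample (25 active), and the power analysis uses 100. Those three statements must be reconciled. If the analysis is in-scanner only, the pooling issue disappears, but power at r = .39 is about 49%.

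**What to change.** 1. Include SCANNING as a fixed term in the Hypothesis 2.1 model, whatever its association with ARI. This costs 1 df of 50 and about 1 power point or less if there is no scanner effect.
2. State in the Randomization section that SCANNING is randomised only among scan-eligible adolescents and that ineligible adolescents are allocated only between active and sham. Restrict any in- versus out-of-scanner contrast to the scan-eligible.
3. Record scan eligibility before allocation, and add a sensitivity analysis of Hypothesis 2.1 in scan-eligible adolescents only. This covers the case that a setting term does not remove.
4. Clarify how the telephone screen fits with the allocation rule and the Section C MRI exclusions, so that it is clear whether and when MRI-ineligible adolescents are enrolled.
5. Reconcile the Hypothesis 2.1 analysis set across the Specific Aims, the hypothesis test and the power analysis.

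The cost is one recorded variable, one regression term, one sensitivity analysis and protocol wording. No extra participants are needed.
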